## Schedule of Events

The table below provides an overview of the schedule of assessments and other tasks that will be completed by subjects in all groups.

Dopaminergic enhancement of rehabilitation therapy early after stroke (TR-Dopa)

Protocol\_20230721

	Must be >14												
Eligibility Checklist		X											
Behavioral Contract	X												
Randomization	X												
Pharmacy – Fill Prescription	X												
MRI Safety Screening Questionnaire	X												
Fugl-Meyer Motor Assessment – Upper Extremity (FMA-UE)		X								X	X	X	
Modified Rankin Scale (mRS)μ		X								X	X	X	
Shoulder Abduction Finger Extension (SAFE) Score		X											
Handedness Inventory		X											
Star Cancellation Test (SCT)		X											
The Language Screening Test (LAST)		X											
Nine Hole Peg Test (NHPT)		X								X	X	X	
Stroke Impact Scale (SIS) – ADL subsection				X*						X	X	X	
SIS – Hand subsection				X*						X	X	X	
Modified Ashworth Scale		X											
Pecs & Biceps													
Review of TR System		X											
Reaction Time Test		X				X 			X 				
Optimization in Primary and Secondary Control (OPS) Scale		X				X			X				
Physical Activity Enjoyment Scale (PACES)		X				X 			X 				
Screening Q re: Restless Legs Syndrome		X			X 2*								
Genetic Testing		X											
TR System Delivery				X (TR Group)								X (UC Group)	
Call UC Subjects (reminder re: participation and logging therapy hours, inquire about adverse events)													
MRI+		X											
Shoulder Pain													
Fatigue													
Daily Motor Assessment													
Finger Tap Assessment													

Every 1-2 weeks

Daily (Start and End of Therapy)

Daily (Start and End of Therapy)

Daily (Start of Therapy)

Daily (Start of Therapy)

Dopaminergic enhancement of rehabilitation therapy early after stroke (TR-Dopa)

Protocol\_20230721

Degree of Perceived Effort		Daily (End of Therapy)								
Stroke Education Quiz		X					X			
Stroke Education		Daily								
Functional Module							X**	X**		
Euro-QoL Visual Analog Scale (VAS)		X						X		
General Anxiety Disorder 7-item Scale (GAD-7)			X							
Medical Outcomes Study (MOS) Social Support Survey (SSS)				X						
Guess Medication					X 					
Brief Resilience Scale						X				
Functional Training Module							X	X		
Patient Satisfaction with TR Survey								X		
TR System Pick-up								X (TR group)		X (UC Group)

^ Only patients in the TR groups will be undergoing TR training for 6 weeks

α Splint permitted for use during BBT for study eligibility only

β Patient must show visible flicker (trace movement) in all 4 movements tested, if BBT not  $\geq 1$

Ω Tally score on day assessment is completed, and contact the patient's care team if the score is high, per SOP guidance

μ At Visit 1, complete pre-stroke and current mRS; current mRS for all other visits

Σ additional question to be asked post-assessment (refer to CRF for details)

\*completed within 5 days after DC home (SIS) or during week 2 (SIS or Restless Leg Screening Q); for UC subjects, the SIS ADL and hand and Restless Leg Screening question will be completed during Week 2, after randomization

completed during start of week

completed during last supervised session of week

+ timing of the MRI may be modified per PI judgment

\*\*schedule 5-10 minutes on supervised days only, to observe practice of functional task related to goal

^^ Visit 5 only applies to participants in the UC group who choose to participate in TR training after their initial study participant has ended

## Screening, Recruitment, and Enrollment

**Recruitment:** Patients will be recruited from two main sources. First, patients with a recent stroke admitted to Cal Rehab, an inpatient rehabilitation facility (IRF) in Los Angeles, CA, will be screened and when appropriate offered study enrollment and a Screening Visit. Second, patients with a recent stroke who have been discharged home then referred to the study will be invited to Cal Rehab for pre-screening and when appropriate study enrollment and a Screening Visit. These referrals may come from outside sites.

Research activities at Cedars-Sinai: One of these referral sites will be Cedars Sinai, who will refer patients as above. Cedars personnel will also assist with (1) reviewing and refining study procedures, and (2) data analysis and results reporting.

**Pre-screening:** Pre-screening will occur before the patient is asked to sign consent. For patients admitted to Cal Rehab, pre-screening will consist of review of the medical record plus a very brief pre-screening exam that aims to identify severe paralysis, severe cognitive or language deficits, or other major abnormalities that clearly indicate that a patient is not eligible for the study. For patients referred to the study from the community, pre-screening will occur during the initial phone call and during a very brief pre-screening exam performed after the patient arrives at Cal Rehab. Patients considered to have a reasonable likelihood of study eligibility will be offered study enrollment. The Screening Visit will then proceed, and this takes place at Cal Rehab.

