## Background

**Patients need higher doses of high-quality rehabilitation therapy:** Stroke remains a leading cause of human disability. Motor deficits are a substantial contributor to this, particularly in the arm: few patients fully recover from arm weakness after a stroke, with the remainder demonstrating persistent arm impairments that are directly linked to larger activity limitations and participation restrictions, lower quality of life, and decreased well-being. Increasing evidence suggests that intensive activity-dependent therapy can improve outcomes after stroke. However, most patients do not receive intensive therapy for reasons that include difficulty traveling to a provider (particularly in the COVID-19 era), shortage of regional rehabilitation care, and poor compliance with assignments.

The amount of rehabilitation therapy received as part of UC is generally small and inconsistent. During the acute stroke admission, the dose of occupational therapy (OT) and physical therapy (PT) provided to a patient varies widely across hospitals. After discharge from the acute admission, the type, location, and dose of rehabilitation therapy are also highly variable.

This is also true in the outpatient setting, where provision of OT and PT after a stroke remains sparse and inconsistent. A study of 23,413 U.S. patients found that during the first 30 days after discharge from the acute stroke admission, 59% did not see an OT or PT at all. A later study of 6,743 adult stroke survivors in the U.S. found that 67% of patients did not receive any outpatient rehabilitation therapy. Medicare generally pays for very few outpatient OT and PT sessions. Outpatient therapy is provided in an inconsistent way, despite the fact that outpatient therapy after stroke has the potential to improve functional status, survival, and quality of life; and to reduce the risk for several psychological disorders. Furthermore, even when patients can access stroke rehabilitation, the amount of therapy provided in standard of care is limited, averaging just 32 arm movements/session, vastly lower than the 600-924 movements/session deemed necessary in animal studies.

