In addition, we will enroll up to 3 patients in a beta study, in which Inclusion criteria 2 and 3 are waived.

## Visit 1

Visit 1 will occur at Cal Rehab. Seven key events occur at Visit 1:

1. [Baseline assessments](#) are completed
2. Blood is drawn for [genetic testing](#)
3. [MRI Screen](#)
4. The patient is [randomized](#)
5. Dispense [study medication](#) (at or shortly after Visit 1)
6. The patient is asked to sign the [behavioral contract](#)
7. The [TR system](#) is introduced.

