## TR Therapy

### The telerehabilitation intervention

**Summary:** Patients are assigned 70 minutes of telerehabilitation (TR) therapy each day, 6 days/week, for 6 weeks, targeting the paretic UE. Functional games and exercises comprise 65 of these daily minutes, and 5 minutes/day is spent on stroke education (which requires targeted arm movement).

Therapy must begin within 7 days of randomization. The first TR session will be a supervised session, whether in-person or via videoconference.

TR is delivered over 36 sessions, each 70-minutes in duration. Of these, 18 sessions are supervised by a licensed OT or PT; for patients receiving TR while admitted to Cal Rehab, the therapist may be in the same room as the patient or communicate via videoconference, and for patients who are at home, the therapist is present via videoconference. The other 18 sessions are unsupervised (i.e., no OT or PT is present at any time during the session; for inpatients at Cal Rehab, the therapist can sit near the patient, with minimal interaction, at the therapist's judgment). Ideally, a given patient will work with the same therapist for the entire 6 weeks. To accommodate possible external events (e.g., illness or family reasons), patients are permitted up to 8 weeks to complete these 36 treatment sessions. In the prior national trial, the FDA determined (Q140628) that the investigation using an earlier generation of the same device was a non-significant risk device study. The FDA made the same determination (Q212693) for the current study. When possible, patients begin TR each day at the time indicated in the behavioral contract. Patients are free to pause between games and activities, as needed. Patients are also instructed to perform all UC that is provided to them—enrollment in this TR study does not interfere with any treatment provided as part of standard of care. A session is considered completed when the patient has completed >50% of the assigned 70 minutes by midnight. After the 36 treatment sessions are completed, or if that does not happen then at the end of 8 weeks, the team retrieves the TR system from the patient's home.

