### Statistical Analysis

We will present descriptive statistics by group for the important covariates including age, site, time from stroke to randomization, MEP status, and hours of outside rehabilitation. We will also report compliance, defined as the percentage of the 36 sessions during which patients complete more than half ( $\geq 36$  min) of assigned activities. For all analyses, data not normally distributed will be appropriately transformed.

Primary efficacy analysis will use the Intent-To-Treat population, consisting of all randomized subjects and multiple imputation for missing data. Secondary analysis will examine the Per-Protocol population, defined as all subjects with complete data who complete  $\geq 36$  minutes of assigned activities on  $\geq 30$  of the 36 therapy sessions over no more than 8 weeks. Analyses will be performed using SAS and R software.

Logistic regression will be used to create a propensity score for treatment group using age, time from stroke to randomization, and total hours of outside rehabilitation therapy from Visit 1 to Visit 4 (or Visit 3 when change is to visit 3). Inverse weights based on this score will be used in secondary analyses to compute adjusted change distributions and corresponding p values. The primary analyses will be based on the inverse propensity score weighted (adjusted) change from base. The corresponding unadjusted changes will also be reported as a secondary analysis. Since this is a randomized trial, we expected the primary propensity adjusted and unadjusted results to be similar.

**Aim 1. TR+UC is superior to UC alone:** A 6-week program of TR targeting arm movement added to UC will result in better arm function as compared to UC alone. The primary endpoint is the change in ARAT score from baseline to 1 month after end of therapy (Visit 4).

The mean differences in ARAT score change from Visit 1 (baseline) to Visit 4 (1 month after end of therapy) will be compared on the log scale using an inverse propensity adjusted t test. A similar method will be used for the secondary change from Visit 1 to Visit 3 (end of therapy). We will first compare the combined TR + UC groups versus the UC group (Aim 1) and then compare TR+Sinemet+UC versus TR+placebo+UC under this model. (Aim 2). As a secondary analysis, we will report the corresponding unadjusted results.

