The difference in ARAT score change between [1] the combined TR group and [2] the UC group will be computed and the distributions compared using ANCOVA, adjusting for Visit 1 ARAT score and propensity score. Specifically, this Aim will compare UC vs. the combined two TR groups (TR+Sinemet plus TR+placebo).

Exploratory analyses will examine whether aphasia or neglect affect TR efficacy by determining if the extent of aphasia (Visit 1 LAST score) or neglect (Visit 1 SCT score), respectively, is correlated with change in ARAT score from Visit 1 to Visit 4. We will use a linear regression model with ARAT change as the outcome, and with treatment group, LAST score, and propensity score as predictors in order to assess the association. This will be repeated using SCT score instead of LAST score. Restricted cubic splines will be used to determine whether the relationships of language screening and neglect to ARAT score change are each linear.

An additional exploratory analysis will examine whether results vary according to the actual TR dose (the total number of arm repetitions across the 36 treatment sessions), using similar regression methods. Sex will also be explored: while females may have poorer functional outcomes after stroke, it is unclear whether the same underlying factors predict that sex will also be associated with a poorer response to rehabilitation therapy.

Analyses will be repeated examining a secondary endpoint, BBT, and then using several tertiary endpoints (FMA-UE, CES-D, mRS, NHPT, SIS-ADL, and SIS-hand). The lead secondary endpoint is the BBT, and this will be analyzed using alpha=0.05. The tertiary endpoints are considered exploratory and will be examined without correction for multiple comparisons. The same statistical methods as above will be used except that the dependent measure will be change from Visit 1 to Visit 4 in each of the secondary/tertiary endpoints. An additional analysis will examine mRS as the dependent variable but instead using a shift analysis (ordinal logistic repeated measures regression) of mRS change score from Visit 1 to Visits 3 and 4.

To aid in the interpretation of the above analyses, additional corollary analyses will repeat above but use as the dependent measure change from Visit 1 to Visit 3. This will be done for the ARAT as well as for the FMA-UE, BBT, mRS, and SIS-hand subsection.

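### Enrolment setting (rehabilitation inpatient or already home) is known before randomization but is in no Aim 1 to 3 model: avoidable loss of precision in Aims 1 and 2, possible confounding in Aim 3

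*Combined protocol and SAP*

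**What the plan says.** Under Screening, Recruitment, and Enrollment the protocol states that "Patients will be recruited from two main sources". One is patients admitted to the rehabilitation facility. The other is "patients with a recent stroke who have been discharged home then referred to the study". Of the second group it adds: "These referrals may come from outside sites". Everyone is assessed and randomized in one place: "Visit 1 will occur at Cal Rehab".

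TR differs by setting at the start. For inpatients, "the therapist may be in the same room as the patient or communicate via videoconference"; for patients at home the therapist appears by videoconference only (The telerehabilitation intervention).

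The randomization sections give a 3:3:2 web-based allocation and no stratification factor. The Statistical Analysis section names "important covariates including age, site, time from stroke to randomization", among others, for descriptive tables. 'Site' is not defined there and does not appear again in the analysis text. The propensity score uses age, time from stroke, and hours of outside therapy from Visit 1 to Visit 4. Aim 1 is also analysed by "ANCOVA, adjusting for Visit 1 ARAT score and propensity score", and Aim 2 repeats the Aim 1 methods. H3A and H3B control for baseline ARAT and the same three clinical measures. None of these models contains enrolment setting.

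**The concern.** Setting is a baseline fact that could predict ARAT change through both sides of the Aim 1 contrast. On the TR side, the early-stroke pilot in the Background gave a median of 6 sessions in the facility, one sixth of a 36-session course. On the usual-care side, inpatients are in a rehabilitation facility, whereas the Background cites a cohort in which, in the 30 days after acute discharge, "59% did not see an OT or PT at all".

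The nearest planned stand-in is outside therapy hours. These accrue between Visit 1 and Visit 4, after assignment, and could be affected by it. Setting is fixed beforehand and has no such problem.

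At stake in Aims 1 and 2 is precision in a trial with no power reserve: 72 patients only just reach 80%, and the plan allows for dropout of up to 20%. In Aim 3 the stake is different, because the predictors are measured and not assigned.

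**Working it through.** **Inputs from the Sample Size section.** Difference 5.7 points, SD 7.4, two-sided alpha 0.05, 27 + 27 + 18 = 72 patients; Aim 1 compares 54 with 18.

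**Assumed, because the documents give neither.** Inpatient share p = 0.50 to 0.85. Gap g = 2, 4 or 6 ARAT points in mean change between settings, meaning the gap left after baseline ARAT, age, time from stroke and therapy hours.

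**Step 1, the plan's own figure.** SE = 7.4 × √(1/54 + 1/18) = 2.01, and 5.7/2.01 = 2.83. Power is 80.8% by the normal approximation and 79.7% by noncentral t on 70 df. The stated 80% with 72 patients reproduces.

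**Step 2, effect of adjusting for setting.** Share of variance removed: R² = p(1−p)g²/7.4². Residual SD = 7.4 × √(1−R²). Power is by noncentral t on 69 df, with one df spent on setting. Example for p = 0.50, g = 4: R² = 0.25 × 16/54.76 = 0.073, residual SD 7.12, power 82.6%.

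| Remaining gap g | R² (p = 0.85 to 0.50) | Aim 1 power | Interval narrower by |
|---|---|---|---|
| 0 | 0 | 79.69% (from 79.71%) | 0 |
| 2 points | 0.9-1.8% | 80.1-80.4% | 0.5-0.9% |
| 4 points | 3.7-7.3% | 81.2-82.6% | 1.9-3.7% |
| 6 points | 8.4-16.4% | 83.0-86.3% | 4.3-8.6% |

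Aim 2 (27 vs 27, borrowing the same 5.7 and 7.4) starts at 79.3% and behaves alike: 80.8-82.2% at g = 4.

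**Step 3, chance imbalance is the same quantity.** The SD of the between-arm difference in inpatient share is √(p(1−p)(1/54 + 1/18)) = 9.7 to 13.6 percentage points. At p = 0.50, g = 6 it moves the Aim 1 estimate with SD 0.136 × 6 = 0.82 points. The unadjusted variance is 2.014² = 4.06 and the adjusted variance is 1.841² = 3.39. The difference, 0.67, equals 0.82². So the imbalance is already inside the unadjusted SE and is not an addition to the loss in step 2.

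**Step 4, Aim 3.** No arithmetic is possible. % CST injury and polygene score are not assigned at random, so if setting were associated with either of them and with ARAT change, omitting it would bias the slope, and the SE would not reflect that. In the drug-by-gene test the drug arm is randomized but the score is not.

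**The case against.** The strongest reply is that this is one more optional covariate. Visit 1 ARAT, age, time from stroke and therapy hours are already planned, entry is limited to ARAT below 32, and these may absorb most of any difference between settings. At a remaining gap of 2 points the gain is under one percentage point of power. The 86.3% figure needs both an even split and a 6-point remaining gap, larger than the 5.7-point target effect. Nor is the contrast between settings absolute: on the pilot's median of 6 facility sessions, most of an inpatient's TR would still be given at home, and the 59% figure describes a general cohort, not this trial's referrals. All of that stands, and it limits the size of the point.

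It does not remove the point. The only planned covariate that tracks care setting closely is measured after randomization, and a term that costs about 0.02 percentage points of power when useless needs little justification.

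A reader might also infer that 'site' is the same for everyone. That is so only if it means place of enrolment. The recruitment section also uses the word for referral origin, which varies, so the supportable statement is that it is undefined and enters no model.

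**Conclusion.** The omission is real and worth correcting, and its size is modest. For Aims 1 and 2 it is an avoidable loss of precision, from less than one to about six or seven percentage points of power across the assumed ranges. The top of that range is an upper bound, and the true position depends on an inpatient share and a remaining gap that the documents do not give.

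Three stronger readings are tempting and unsupported. First, that the randomized comparisons are biased or the type I error inflated: randomization protects both, and the SE already covers chance imbalance. Second, that the stated power is wrong: it reproduces, and 7.4 is an SD without adjustment for setting. Third, that Aim 3 suffers from chance imbalance: its predictors are not randomized, so the issue there is possible confounding. The documents show no link between setting and either predictor, so that remains a possibility and not a demonstrated bias.

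**What to change.** Before unblinding, amend the Statistical Analysis section as follows.

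- Define setting at randomization as one binary baseline variable: rehabilitation inpatient or living at home.
- Enter it directly in the Aim 1 and Aim 2 ANCOVA and in the H3A and H3B regressions.
- Include it in the propensity model that supplies the weights for the t test. If the ANCOVA keeps the propensity score as well, say that the direct term is the intended adjustment for setting.
- Keep 'site' in the descriptive list, but say whether it means place of enrolment or referral origin.
- Tabulate setting by arm.
- Treat any Aim 1 difference by setting as descriptive only. At 85% inpatients, about 18 × 0.15 = 2.7 UC patients would come from home.

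The cost is SAP wording and one degree of freedom per model. Setting is known at enrolment, so no new visit, assessment or sample size is needed. If randomization is still open to change, stratifying by setting is an alternative.

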## Enrollment

The initial steps of study enrollment are as follows:

- Provide the patient with an overview of the study and the study timeline
- Have the patient sign the ICF and the Health Insurance Portability and Accountability Act (HIPAA) Research Authorization for Release of Protected Health Information (PHI)
- Provide the patient with a copy of the Research Participant's Bill of Rights
- Gather demographic data, medical history, and contact information, from the patient, from a subsequently obtained copy of medical records, and when possible from the electronic health record
- Complete baseline screening measures to confirm study eligibility, including:
  - **Action Research Arm Test (ARAT)**
  - **Box and Blocks Test (BBT)**

**If unable to complete BBT, will examine wrist extension and finger flexion for a visible flicker** (at least trace contraction must be present for both movements)

- **Examine range of motion against gravity in the paretic shoulder and elbow**
- **3 Rehabilitation Practice Tasks**
- **Center for Epidemiologic Studies Depression Scale (CES-D, 10 questions)**
- **Montreal Cognitive Assessment (MoCA)**
- **Trail Making Test (TMT): Part A**
- **Visual Acuity Screen**
- Complete the Eligibility Checklist, which evaluates whether the patient fully meets inclusion and exclusion criteria
- If the patient is an inpatient at Cal Rehab, enter a research progress note into the electronic health record (Epic)

The Screening Visit may be broken into more than one session, as needed.

If the patient meets all of the eligibility criteria and is amenable to study participation, they will be given a Visit 1 follow-up appointment, ideally on the next day.

